#### **6.4.2** Missing Time Information for Adverse Events

If the AE start or end time is missing, it will not be imputed.

#### 6.4.2.1 Partial AE Start Date

#### 6.4.2.1.1 Missing day and month

If the year is the same as the year of the date of the first dose of study medication, then the day and month of the date of the first dose of study medication will be assigned to the missing fields.

If the year is before the year of the date of the first dose of study medication, then 31 December will be assigned to the missing fields.

If the year is after the year of the date of the first dose of study medication, then 01 January will be assigned to the missing fields.

#### 6.4.2.1.2 Missing month only

The day will be treated as missing and both month and day will be replaced according to the above procedure.

#### **6.4.2.1.3** Missing day only

If the month and year are the same as the month and year of the date of the first dose of study medication, then the day of the first dose of study medication will be assigned to the missing day.

If either the year is before the year of the date of the first dose of study medication or if both years are the same but the month is before the month of the date of the first dose of study medication, then the last day of the month will be assigned to the missing day.

If either the year is after the year of the date of the first dose of study medication or if both years are the same but the month is after the month of the date of the first dose of study medication, then the first day of the month will be assigned to the missing day.

If the imputed AE start date is after the AE stop date, then the imputed AE start date will be set to the AE stop date.

#### 6.4.3 Missing Date Information for Concomitant Medications

If the medication start date is missing, and the medication stop date is on or after the first dose of study medication, then the medication start date will be imputed as the date of the first dose of study medication.

If the medication start date is missing, and the medication stop date is not missing and before the first dose of study medication, then the medication start date will be imputed as the medication stop date.

#### 6.4.3.1 Partial Medication Start Date

#### 6.4.3.1.1 Missing day and month

If the year of the incomplete start date is the same as the year of the date of the first dose of study medication, then the day and month of the date of the first dose of study medication will be assigned to the missing fields.

If the year of the incomplete start date is before the year of the date of the first dose of study medication, then 31 December will be assigned to the missing fields.

If the year of the incomplete start date is after the year of the date of the first dose of study medication, then 01 January will be assigned to the missing fields.

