#### 6.4.3.1.2 Missing month only

The day will be treated as missing and both month and day will be replaced according to the above procedure.

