#### **6.4.3.1.3** Missing day only

If the month and year of the incomplete start date are the same as the month and year of the date of the first dose of study medication, then the day of the first dose of study medication will be assigned to the missing day.

If either the year is before the year of the date of the first dose of study medication or if both years are the same but the month is before the month of the date of the first dose of study medication, then the last day of the month will be assigned to the missing day.

If either the year is after the year of the date of the first dose of study medication or if both years are the same but the month is after the month of the date of the first dose of study medication, then the first day of the month will be assigned to the missing day.

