#### 6.5 Appendix 5: Prior Medications and Concomitant Medications

The definitions for prior and concomitant medications for the sub-study are found in Table 9. The assignments will be made relative to the date/time of the first dose of TM BUP.

Note that a given medication may be considered both prior and concomitant depending on missing start and end dates/times, under these definitions. Therefore, the prior/concomitant medication categories are not mutually exclusive.

Table 9. Definitions of Prior and Concomitant Medications

	Start Date/Time of Non-Study Medication			
End Date/Time of Non-Study Medication	Missing a	< Start date/time of Study Medication b	≥ Start date/time of Study Medication b and <end date="" time
of study medicationb</end>	≥ end date/time of study medication b
Missing (includes flagged as 'Ongoing') a	Prior Concomitant	Prior Concomitant	Concomitant	Not a sub-study medication
< Start date/time of Study Medication b	Prior	Prior	Data Error	Data Error
≥ Start date/time of Study Medication b	Prior Concomitant	Prior Concomitant	Concomitant	Data Error

a If the time is missing, then only the date will be used. See Section 6.4.3 for handling of missing date information

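### SAP 6.4.3.1 imputes partial medication start dates without checking the stop date, so some medications that ended before the first dose are labelled Data Error or Concomitant instead of Prior

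*SAP*

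**What the plan says.** SAP 6.4.3.1 fills in partial medication start dates by reference to the first dose of study medication. If day and month are missing, the condition in 6.4.3.1.1 is "If the year of the incomplete start date is the same as the year of the date of the first dose of study medication", and the first-dose day and month are then used. If only the month is missing, 6.4.3.1.2 sends the record to the same rule: "The day will be treated as missing and both month and day will be replaced according to the above procedure". If only the day is missing and the month and year match the first dose, 6.4.3.1.3 says "then the day of the first dose of study medication will be assigned to the missing day". Starts in an earlier month or year are set to the end of that month or year.

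The adverse event rules in 6.4.2.1 follow the same steps but end with a check on date order: "If the imputed AE start date is after the AE stop date, then the imputed AE start date will be set to the AE stop". The medication start rules have no such sentence. SAP 6.4.3 keeps the order for a wholly missing start when the stop precedes the first dose: "then the medication start date will be imputed as the medication stop date". SAP 6.4.3.2 has an ordering rule, but it acts only on an imputed stop date, which it moves forward to the start date.

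Table 9 in SAP 6.5 then assigns the labels relative to the first dose of TM buprenorphine. An end before study medication with a start on or after it is a Data Error. The same end with an earlier or missing start is Prior. Footnote a refers missing dates back to 6.4.3. SAP 5.7.1 summarises prior and concomitant medications under these definitions.

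**The concern.** Both sets of rules fill a partial start with the first-dose date, but only the adverse event rules check the result against the stop date. For a medication known to have ended before the first dose, that fill cannot be right, because a start cannot follow its own stop. The label then reflects the imputation and not the participant's history.

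Such records can occur. The screening schedule (Protocol Appendix 22.1) collects medications taken within 30 days before consent, and screening lasts up to 30 days, so medications that stopped before the first dose will be in the database. What is at stake is whether the by-arm tables of prior and concomitant medications say what they claim to say.

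**Working it through.** The plan gives no figure to reproduce, so the check is to apply the rules as written to example records.

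Illustrative inputs: first dose 20 May 2022, last dose 24 June 2022. The collection window goes back to 20 May − 30 days of screening = 20 April, then − 30 days of look-back = 21 March 2022. Every stop date below lies inside it.

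Rules applied:
- Start, day and month missing: same year as first dose → first-dose date; earlier year → 31 December.
- Start, day missing: same month as first dose → first-dose date; earlier month → last day of that month.
- Stop, day missing, month before the last-dose month → last day of that month.
- An imputed stop before the start → moved to the start.
- Proposed check: imputed start = the earlier of imputed start and stop.

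| Record | Start recorded | Stop recorded | Imputed start | Stop used | Label as written | Start with check | Label with check |
|---|---|---|---|---|---|---|---|
| A | May 2022 | 10 May 2022 | 20 May 2022 | 10 May 2022 | Data Error | 10 May 2022 | Prior |
| B | 2022 | 10 May 2022 | 20 May 2022 | 10 May 2022 | Data Error | 10 May 2022 | Prior |
| C | April 2022 | 20 April 2022 | 30 April 2022 | 20 April 2022 | Prior | 20 April 2022 | Prior |
| D | 2021 | 10 May 2022 | 31 Dec 2021 | 10 May 2022 | Prior | 31 Dec 2021 | Prior |
| E | 2022 | April 2022 | 20 May 2022 | 30 April, then moved to 20 May 2022 | Concomitant | 30 April 2022 (stop stays 30 April) | Prior |

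A and B: any true start is on or before 10 May, so Prior is the only possible label. C: the imputed start is 10 days after the stop, but both dates precede the first dose and the label is right. An earlier-year start whose stop falls in that same year behaves like C. D: the order is kept. E: the medication ended in April, yet the 6.4.3.2 rule carries its stop to the first-dose date. With the check applied first, that rule has nothing to move.

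To show how the two kinds of partial date differ, the rules were enumerated over assumed dates: every first-dose day in 2022, stop 1 to 60 days before it, true start 0 to 30 days before the stop, all combinations weighted equally. These assumptions are not in the documents, and the shares apply only to records that already have a partial start and a complete stop before the first dose.

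| Missing part of start | Imputed start after stop | Data Error | Data Error with check |
|---|---|---|---|
| Day and month | 95.6% | 87.5% | 0% |
| Day only | 47.5% | 8.3% | 0% |

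A related point is a wholly missing start with a stop on or after the first dose. Under 6.4.3, "then the medication start date will be imputed as the date of the first dose of study medication", which Table 9 would read as Concomitant only (provided that date precedes the last dose). Table 9's Missing-start column gives Prior and Concomitant for the same record. If imputation always came first, two of the three cells in that column (end before, and end on or after, the first dose) could never be used. The SAP does not state the order.

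**The case against.** The best answer is that this is housekeeping. A programmer who sees a Data Error label would look at the record, and could place partial starts in Table 9's Missing column, which gives Prior for A and B. Protocol 13.2 also provides computerised and manual checks and queries for apparent errors.

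Part of this stands. The label is visible for A and B, and nothing in SAP 5.7.1 or 6.5 says that Data Error records are removed. A reader might infer that real prior medications drop out of the tables, but the documents do not say so. The rest does not answer the point. Footnote a sends missing dates to 6.4.3, where partial starts are imputed, so the Missing column is not their natural place. A query helps only if the site can supply the missing part of the date. Record E carries no warning, because it looks like an ordinary concomitant medication.

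A reader might also infer that long-standing medications with an unknown start lose their Prior label. The text does not establish that. It follows only if imputation precedes Table 9, and the note above the table points the other way: "a given medication may be considered both prior and concomitant depending on missing start and end dates/times". The fair statement is that the order is ambiguous.

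**Conclusion.** The rule is wrong as written, within a narrow scope. Data Error arises only when the stop date is complete and before the first dose, and the partial start shares the first-dose year (day and month missing, or month missing) or the first-dose month (day missing). It would be too strong to say that every partial start is mislabelled, since records such as C and D come out right. The Concomitant error needs both dates to be partial.

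The consequence is small. In the visible text it is confined to the descriptive summaries of SAP 5.7.1. No primary or secondary endpoint, analysis population or decision rule uses Table 9. SAP 5.5.2, which 5.7.6 identifies as concomitant medications, is not visible in the public document, so nothing is claimed about it. The number of affected records is not known, and the enumerated shares are not a forecast. The conclusion rests on applying 6.4.3 before Table 9 for partial dates, as footnote a directs.

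**What to change.** 1. Add to SAP 6.4.3.1, after all partial-start rules: an imputed medication start that falls later than the stop date, whether that stop is recorded or imputed, is reset to the stop date.
2. State the order. Impute partial stops and starts, apply the new check, then apply the 6.4.3.2 ordering rule only where the start date is fully known. Without this, the two rules pull in opposite directions when both dates are partial, and the result for a record like E depends on which runs first.
3. State whether Table 9's Missing-start column uses the date as recorded, before 6.4.3 fills it. Using the recorded date keeps all cells of that column in use.

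The cost is about three sentences in the SAP and a few lines of code. The one thing to note is that a reset record has equal start and stop dates, so its imputed duration should not be interpreted. SAP 5.7.1 does not summarise duration.

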#### 6.4.3.1.2 Missing month only

The day will be treated as missing and both month and day will be replaced according to the above procedure.

#### **6.4.3.1.3** Missing day only

If the month and year of the incomplete start date are the same as the month and year of the date of the first dose of study medication, then the day of the first dose of study medication will be assigned to the missing day.

If either the year is before the year of the date of the first dose of study medication or if both years are the same but the month is before the month of the date of the first dose of study medication, then the last day of the month will be assigned to the missing day.

If either the year is after the year of the date of the first dose of study medication or if both years are the same but the month is after the month of the date of the first dose of study medication, then the first day of the month will be assigned to the missing day.

#### 6.4.3.2 Partial Medication Stop Date

If a medication stop date is missing and the ongoing status is also missing, then the medication is assumed to be ongoing.

If the imputed medication stop date is before the medication start date (whether imputed or non-imputed), then the imputed medication stop date will be equal to the medication start date.

#### 6.4.3.2.1 Missing day and month

If the year of the incomplete stop date is the same as the year of the date of the last dose of study medication, then the day and month of the date of the last dose of study medication will be assigned to the missing fields.

If the year of the incomplete stop date is before the year of the date of the last dose of study medication, then 31 December will be assigned to the missing fields.

If the year of the incomplete stop date is after the year of the date of the last dose of study medication, then 01 January will be assigned to the missing fields.

#### 6.4.3.2.2 Missing month only

The day will be treated as missing and both month and day will be replaced according to the above procedure.

### 6.4.3.2.3 Missing day only

If the month and year of the incomplete medication stop date are the same as the month and year of the date of the last dose of study medication, then the day of the last dose of study medication will be assigned to the missing day.

If either the year is before the year of the date of the last dose of study medication or if both years are the same but the month is before the month of the date of the last dose of study medication, then the last day of the month will be assigned to the missing day.

If either the year is after the year of the date of the last dose of study medication or if both years are the same but the month is after the month of the date of the last dose of study medication, then the first day of the month will be assigned to the missing day.

#### 6.4.4 Missing Time Information for Prior/Concomitant Medications

If the start or end time is missing, it will not be imputed.

#### 6.5 Appendix 5: Prior Medications and Concomitant Medications

The definitions for prior and concomitant medications for the sub-study are found in Table 9. The assignments will be made relative to the date/time of the first dose of TM BUP.

Note that a given medication may be considered both prior and concomitant depending on missing start and end dates/times, under these definitions. Therefore, the prior/concomitant medication categories are not mutually exclusive.

Table 9. Definitions of Prior and Concomitant Medications

	Start Date/Time of Non-Study Medication			
End Date/Time of Non-Study Medication	Missing a	< Start date/time of Study Medication b	≥ Start date/time of Study Medication b and <end date="" time
of study medicationb</end>	≥ end date/time of study medication b
Missing (includes flagged as 'Ongoing') a	Prior Concomitant	Prior Concomitant	Concomitant	Not a sub-study medication
< Start date/time of Study Medication b	Prior	Prior	Data Error	Data Error
≥ Start date/time of Study Medication b	Prior Concomitant	Prior Concomitant	Concomitant	Data Error

a If the time is missing, then only the date will be used. See Section 6.4.3 for handling of missing date information

#### 6.6 Appendix 6: Medical History

The number and percentage of participants reporting medical history events will be tabulated by SOC and PT, by decreasing frequency, for the SFAS using descriptive statistics and observed data.

#### 6.7 Appendix 7: Customised MedDRA Queries

The CMQs included below are based on MedDRA v24.1. These terms will be reviewed against the version of MedDRA used for reporting (see Section 5.1.1), and updated if needed.

## 6.7.1 Customised MedDRA Query (CMQ) List of Preferred Terms for Drug Related Hepatic Disorders

Table 10. Customised MedDRA Query (CMQ) List of Preferred Terms for Drug Related Hepatic Disorders

Cholestasis and jaundice of hepatic origin		
Bilirubin excretion disorder	Jaundice	
Cholaemia	Jaundice cholestatic	
Cholestasis	Jaundice hepatocellular	
Cholestatic liver injury	Mixed liver injury	
Cholestatic pruritus	Ocular icterus	
Drug-induced liver injury	Parenteral nutrition associated liver disease	
Hepatitis cholestatic	Deficiency of bile secretion	
Hyperbilirubinaemia	Yellow skin	
Icterus index increased		
Hepatic failure, fibrosis and cirrhosis and other liver damage-related conditions		
Acute hepatic failure	Liver and small intestine transplant	

b Study medication includes both TM BUP and RBP-6000, start date/time of study medication is the date/time of first dose of TM BUP in the induction phase, end date/time of study medication is the date/time of the last administration of TM BUP or RBP-6000 (injection 1,2, or 3), whichever is the last.

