8.9. Other Analyses

Additional details of these other analyses will be provided in the SAP.

Demographic and disease characteristics at Screening (e.g., sex, race, age, weight, and BMI) will be summarised for the SFAS overall and by induction arm using descriptive statistics.

Results of UDS and TLFB on the first induction day will be summarised by substance for the SFAS overall and by induction arm, for the UDS and TLFB assessments separately and combined across both assessments using descriptive statistics.

The number and percentage of participants taking concomitant medications (any medication and medications to treat withdrawal symptoms) during the time period from the first dose of TM buprenorphine through Injection 2 will be summarised for the SFAS overall and by induction arm overall and within individual randomisation stratum using descriptive statistics.

The COWS scores at each timepoint and visit during the OLTP will be summarised overall, and by induction arm overall and within individual randomisation stratum using descriptive statistics; the difference in group mean will be estimated with a 95% CI for each timepoint and visit.

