#### **5.4.2.1** Definition of endpoints

These endpoints will encompass all induction attempts, and therefore utilise the first dose of TM BUP for derivations. A treatment-emergent adverse event (TEAE) is defined as an AE having an onset date/time after administration of the first TM BUP dose and before the date/time of Injection 3. The TEAEs are classified into the 2 consecutive time intervals, defined as:

• TEAEs up to RBP-6000 Injection 2 are TEAEs with a start date/time on or after the first dose of TM BUP and before the date/time of Injection 2

 TEAEs between RBP-6000 Injections 2 and 3 are TEAEs with a start date/time on or after Injection 2 and before the date/time of Injection 3

Note: If AE onset time is missing, then only the onset date will be used to assign TEAE status. An AE onset date on or after the date of the administration of the first dose of TM BUP will be considered a TEAE.

For participants who received Injections 1 and 3 (but not Injection 2), their TEAE with start date before the date of Injection 3 will be classified into the time interval of "up to RBP-6000 Injection 2". For discontinued participants whose last injection was Injection 1, their TEAE with start date after the last injection will be classified into the time interval of "up to RBP-6000 Injection 2". For discontinued participants whose last injection was Injection 2, their TEAE with start date after the last injection will be classified into the time interval of "between RBP-6000 Injections 2 and 3".

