#### 5.7 Other Analyses

#### 5.7.1 Concomitant Medications, Other

The number and percentage of participants taking any concomitant medication during the time period from the first dose of TM BUP up to Injection 2 will be summarised by pharmacological group (ATC level 3) and preferred drug name for the SFAS overall and by induction arm overall and within individual randomisation strata using descriptive statistics. These analyses will include concomitant medications from all induction attempts that have a start date/time before the date/time of Injection 2.

The number and percentage of participants taking any prior medications and concomitant medications (Section 6.5) will be summarised by pharmacological group (ATC level 3) and preferred drug name for the SFAS overall and by induction arm overall and within individual randomisation strata using descriptive statistics.

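### SAP Table 9 closes the concomitant-medication window at the last study dose, so valid records from participants who leave before Injection 3 are labelled errors or out of scope

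*SAP*

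**What the plan says.** SAP Appendix 5 (Section 6.5) states that "The assignments will be made relative to the date/time of the first dose of TM BUP". Table 9 crosses the start of each medication with its stop. Footnote b defines the far end of the window: the "end date/time of study medication is the date/time of the last administration of TM BUP or RBP-6000", whichever comes last, with Injections 1 to 3 in scope.

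The right-hand column covers medications that start on or after that last dose. If the stop is missing or ongoing, the cell reads "Not a sub-study medication". If the stop falls on or after the first study dose, the cell reads *Data Error*.

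SAP 5.7.1 contains two summaries. The second cites Table 9's section: participants "taking any prior medications and concomitant medications (Section 6.5) will be summarised by pharmacological group" and preferred drug name. The first runs from the first TM BUP dose up to Injection 2 and has its own rule: "These analyses will include concomitant medications from all induction attempts that have a start date/time before the date/time of Injection 2". It does not cite Section 6.5.

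For adverse events, SAP 5.4.2.1 has a specific rule for leavers: "For discontinued participants whose last injection was Injection 1, their TEAE with start date after the last injection will be classified" into the interval up to Injection 2. A parallel rule places events after a last Injection 2 in the interval between Injections 2 and 3.

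**The concern.** For a participant who completes the sub-study, the last dose is Injection 3, which is also where the sub-study ends, so footnote b works. For a participant who leaves earlier, the last dose comes before the end of observation. Protocol 9.1.1 describes an injection that releases drug over 4 weeks. Protocol 6.7.2 encourages an ET visit 4 weeks after the last injection. Protocol 9.9 collects concomitant medications through the end-of-treatment visit. The data therefore exist, and Table 9 leaves them out.

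Two things follow. A medication that starts and stops after the last dose is an ordinary record, yet it is labelled an error. And an adverse event after the last injection can be tabulated while the medication given for it is not counted as concomitant. The sub-study's secondary objective is safety and tolerability, and Protocol 9.13 asks investigators to identify medications given for withdrawal symptoms. A summary that stops at different points for leavers and completers, and possibly for the two arms, is harder to read for that purpose.

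**Working it through.** The plan gives no figure for this point. The check applies Table 9 to example timelines and then sizes the group at risk.

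**1. Rule applied.** Let S0 be the first TM BUP dose and E0 the last TM BUP or RBP-6000 dose. For a medication starting at s on or after S0:
- s < E0, with the stop missing or on or after S0: concomitant.
- s ≥ E0, stop missing or ongoing: not a sub-study medication.
- s ≥ E0, stop on or after S0: Data Error.

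**2. Timelines.** Times are hours from the first TM BUP dose. They are illustrative assumptions, with one induction attempt each.

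| Participant | E0 | Medication | Table 9 result |
|---|---|---|---|
| Rapid induction, Injection 1 at 1 h, then leaves | 1 | 3 to 27 | Data Error |
| Same | 1 | 3, ongoing | Not a sub-study medication |
| Rapid induction, Injection 1 at 1 h, extra TM BUP at 4 h | 4 | 3 to 27 | Concomitant |
| Rapid induction, one TM BUP dose only | 0 | 0.5 to 2 | Data Error |
| SoC, TM BUP to 72 h, then leaves | 72 | 3 to 27 | Concomitant |
| Same | 72 | 80 to 100 | Data Error |
| Injections 1 and 2 (169 h), then leaves | 169 | 200 to 220 | Data Error |
| Completer, Injection 3 at 840 h | 840 | 3 to 27 | Concomitant |
| Same | 840 | 900 to 1000 | Data Error |

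In the last row, excluding the record from the sub-study is correct. Only the label is wrong.

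**3. Difference by arm.** SAP 5.1.4 places Injection 1 about 1 hour after TM BUP in the rapid arm and about 7 to 14 days after Induction Day 1 in the SoC arm. For participants whose last dose is Injection 1, the window is therefore about 1 hour or about 7 to 14 days. A medication started 3 hours after the first TM BUP dose is outside the first window and inside the second. A medication started after Injection 1 is outside in both arms, so the difference lies in time since the first TM BUP dose.

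**4. Adverse events side by side.** In the first row of the table, an event at 3 h is a TEAE in the interval up to Injection 2 under SAP 5.4.2.1. A medication started for it at the same hour is a Data Error under Table 9.

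**5. Size of the group at risk.** Sub-study Section 5 (Protocol Appendix 22.9) assumes at least 20% loss before Injection 3. Check on its enrolment figure: 390 / 0.80 = 487.5, or 488, against 489 in the plan.
- At 20%: 0.20 × 489 = 97.8, about 98. At 2:1 (326 and 163) this is 0.20 × 326 = 65 rapid and 0.20 × 163 = 33 SoC.
- The power calculation assumes 70% retention at Injection 2. On that figure 0.30 × 489 = 146.7, about 147 not retained (98 rapid, 49 SoC), before any loss between Injections 2 and 3.

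These are participants to whom the early cut-off would apply. How many start a medication after their last dose is not given. Nor are the counts restricted to the SFAS, the population for the summary.

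**The case against.** A reader might infer that withdrawal treatment in early leavers is lost. The documents do not support that, for four reasons.

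- Only medications started on or after the last dose are affected. Those started earlier and continued stay concomitant, and extra TM BUP on Day 1 moves the cut-off later.
- The first summary in SAP 5.7.1 has its own start-date cut and may well include these medications. Protocol Appendix 22.9, Section 8.9 plans summaries of "any medication and medications to treat withdrawal symptoms) during the time period from the first dose of TM buprenorphine through Injection 2". SAP 5.7.6 points to Section 5.5.2 for concomitant medications, and that text is not in the public SAP. The withdrawal-medication analysis may sit there and cannot be checked.
- SAP 5.1.2 keeps all data collected up to the Injection 3 Visit in the listings, including end-of-study visits before it. Nothing is deleted.
- Tolerability is assessed mainly through the adverse event endpoints, including withdrawal events, and these keep events after the last injection. The medication summary is descriptive.

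A reader might also infer that the participants who leave had the worst withdrawal, so that the omission flatters one arm. That is plausible, but nothing in the documents establishes it.

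All of this stands and limits the consequence. It does not rescue the table. Section 6.5 presents its definitions as those for the sub-study, and the SAP does not say whether they also filter the first 5.7.1 summary. Nor does it say where that summary ends for someone who never receives Injection 2. For participants who leave after Injection 2, no other visible tabulation covers later medication.

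**Conclusion.** The point holds as a defect in Table 9 and in the one visible summary that cites Section 6.5. For participants who discontinue before Injection 3, the window closes too early, valid records are labelled errors, and the rule does not match the TEAE rule. The cut-off can differ by arm.

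At most about 98 of 489 participants are at risk at the planned 20% loss, or about 147 or more if retention at Injection 2 is the 70% used for power. Both figures rest on the plan's attrition assumptions and count people at risk, not people affected. Severity is minor: the summary is descriptive, the records stay available, and no decision rule depends on it.

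**What to change.** 1. In footnote b, keep Injection 3 as the end of the window for completers. For participants who discontinue, end it at the ET visit or last sub-study contact, in line with SAP 5.4.2.1.
2. In the column for medications starting on or after the last dose, classify records as concomitant inside that window and as not a sub-study medication after it, whether or not they have a stop date. Keep *Data Error* only where the stop precedes the start.
3. Add a sentence saying whether Table 9 also governs the first summary in SAP 5.7.1 and where that summary ends for participants who never receive Injection 2. Confirm the same for Section 5.5.2.

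The cost is one footnote, one column of cells and a sentence or two, plus the matching change in the derivation program. No new data are needed.
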